Evaluation of the effect of the “Eat Less Meat” one-month challenge on meat consumption among French university students

Date: January 31st, 2023

Principal Investigator: [name]

Description:

In a context where meat consumption should be dramatically reduced in western countries to improve both population and planet health, the “Eat Less Meat” one-month challenge is a new behavioural intervention that aims (i) to weaken meat consumption habit and (ii) to enhance intrinsic motivation to eat less meat to trigger long-term reduction in meat consumption. The present registration focusses on the quantitative evaluation of the effect of this challenge on university student’s meat consumption.

STUDY INFORMATION

Hypotheses

Main hypothesis:

H1: The “Eat Less Meat” challenge will have decreased meat consumption in participants during the challenge and 3 months after challenge completion compared to before.

Secondary hypotheses:

H2: The “Eat Less Meat” challenge will have increased (resp. decreased) nutritional quality (resp. environmental impact) of the diet in participants during the challenge and 3 months after challenge completion compared to before.

H3: The “Eat Less Meat” challenge will have weakened meat consumption habits in participants during the challenge and 3 months after challenge completion compared to before.

H4: The “Eat Less Meat” challenge will have increased health, ethics and animal welfare motivations for food choices in participants during the challenge and 3 months after challenge completion compared to before.

Study design

Parallel two-arm randomized controlled trial with repeated measures (online questionnaires) pre-, during- and post-intervention. All the participants will be recruited to take part in the “Eat Less Meat” challenge for one month. Participants in the control group will take part in the challenge 3 months after the participants in the intervention group. Participants in both groups will complete the online questionnaires at the exact same time, i.e., pre-, during- and post-intervention measures will take place before the control group starts the challenge. A figure summarizing the study design is available in **Appendix 1**.

Randomization

A 1:1 randomisation sequence will be generated before recruitment using the Random Allocation software¹ to allocate each participant to one of the experimental arm (control or intervention).

SAMPLING PLAN

Data collection procedures

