¹ Mahmood Saghaei, ‘Random Allocation Software for Parallel Group Randomized Trials’, *BMC Medical Research Methodology*, 4 (2004), 1–6 <<https://doi.org/10.1186/1471-2288-4-26>>.

Inclusion criteria.

- Aged ≥ 18
- BMI ≥ 18.5
- University student in 'Bourgogne Franche-Comté'
- Fluent in French
- Available email address
- Available Instagram profile
- Not vegetarian or vegan or pescatarian
- Not pregnant/breastfeeding
- No iron deficiency

Brief description of the "Eat Less Meat" challenge.

Participants will be recruited through social media, emails, flyers and posters on campus to take part in the "Eat Less Meat" challenge; recruitment materials will mention that the challenge is part of a research study. Eligible participants that will give their informed consent will be able to choose their goal for the challenge for one month: (i) no meat, (ii) meat 3 times a week, (iii) meat 6 times a week (which will need to be lower than current consumption) and will be enrolled in the challenge. The 'meat category' includes all red meat and poultry but not fish or other animal-sourced food products (eggs, dairy, etc.). The first day of the challenge, the participants will receive by email a cookbook of easy-to-prepare and cheap meat-free recipes and a starter kit with advices and motivational tips, then they will receive an email each week with more advices and motivational tips. Participants will be also asked to follow the Instagram account of the challenge where during one month (i) one post will be posted each day, (ii) engaging stories requiring interactions will be posted regularly, (iii) participants can ask their questions to the research team, (iv) participants can interact with each other's. The Instagram posts will cover three main topics: (i) knowledge about meat and its impact on health and environment, (ii) tips for meat-free cooking, (iii) social/contextual pressure to eat meat and how to avoid it. Emails and posts will aim at keeping the participants engaged in the one-month challenge and to enhance their intrinsic motivation to eat less meat.

Data collection for evaluation.

Eligible participants will be informed that their participation will involve completing a first online questionnaire on sociodemographics at the point of inclusion (10 min) and then three other online questionnaires at three time points: pre-, during- and post-intervention (30 min each time, 10€ compensation).

Sample size

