As a minimum, we will aim to recruit 200 university students willing to take part in the challenge but we will include in the study all voluntary students that will register. Registrations will close the day before the challenge starts for the intervention group.

Sample size rationale

The sample size was determined based on a power analysis (GPower v3.1) to detect a small effect size of $f=0.10$ for a within-between interaction in a mixed model with 3 repeated measures. A total sample size of 164 participants was necessary to reach 0.80 power at 0.05 alpha. Considering an attrition rate in between 15 and 20%, we will aim to recruit 200 university students willing to take part in the challenge.

VARIABLES

Manipulated variables

We will manipulate whether participants will be assigned to intervention or control group (challenge 3 months after the intervention group). It will be coded as a binary variable: 'intervention' or 'control' at the participant level.

Measured variables

The sociodemographics questionnaire will record age, gender, scholarship status, educational level, field, parents' educational level, place of living, dieting status and type of diet.

The evaluation questionnaires will record three types of variables at the three time points:

- Food consumption frequency

The food frequency questionnaire (FFQ) will include 109 foods, 12 non-alcoholic drinks and 4 alcoholic drinks with frequency assessed by a 6-item scale from "Never" to "Several times a day"². Participants will estimate their usual portion size for 75 food items using photos on a 5-point scale derived from the SU.VI.MAX portion book³. For the 50 remaining food items, we will use the standard portion size. Consumption frequencies of each item will be transformed into daily frequencies and daily intake will be calculated by multiplying the daily frequency by the estimated portion size. Individual nutrients intake will then be calculated for all the participants before and during the lockdown by multiplying the daily intake of each food item by the nutritional values from the SU.VI.MAX nutrient composition database⁴. Participants will be asked about their food consumption for the month before questionnaire completion, i.e., the month before the challenge, the month of the challenge and the third month after the challenge for the intervention group (all the measures will take place before the control group start the challenge).

- Meat consumption habit

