The strength of meat consumption habit will be assessed using the Self-Report Habit questionnaire⁵ including 12 items accompanied by a 6-point response scale anchored by 'strongly disagree' and 'strongly agree' from 1 to 6. The scores will be coded such that high values indicated strong habits. Participants will be asked about their meat consumption habit at the time of questionnaire completion.

- Food choice motives

The food choice questionnaire (FCQ) will be the adapted French version of the Food Choice Questionnaire⁶. It includes 30 items and 10 subscales: health, mood, convenience, sensory appeal, natural content, price, weight control, familiarity, ethical concern and animal welfare. Answers to each item will range from 1 to 4: 1 = Not at all important; 2 = A little important; 3

² Manik Kadawathagedara and others, 'Diet during Pregnancy: Influence of Social Characteristics and Migration in the ELFE Cohort', *Maternal and Child Nutrition*, 17.3 (2021), 1–13 <<https://doi.org/10.1111/mcn.13140>>.

³ S Hercberg, M Deheeger, and P Preziosi, *SU.VI.MAX. Portions Alimentaires : Manuel Photos Pour l'estimation Des Quantités*, Economica (Paris, 2002).

⁴ S Hercberg, *Table de Composition Des Aliments SU.VI.MAX*, Economica (Paris, 2006).

⁵ Bas Verplanken and Sheina Orbell, 'Reflections on Past Behavior: A Self-Report Index of Habit Strength', *Journal of Applied Social Psychology*, 33.6 (2003), 1313–30 <<https://doi.org/10.1111/j.1559-1816.2003.tb01951.x>>.

⁶ Muriel C.D. Verain and others, 'Sustainable Food Choice Motives: The Development and Cross-Country Validation of the Sustainable Food Choice Questionnaire (SUS-FCQ)', *Food Quality and Preference*, 93 (2021), 104267 <<https://doi.org/10.1016/j.foodqual.2021.104267>>; [name] and others, 'Food Choice Motives and the Nutritional Quality of Diet during the COVID-19 Lockdown in France', *Appetite*, 157 (2021), 105005 <<https://doi.org/10.1016/j.appet.2020.105005>>.

= Moderately important; 4 = Very important. Participants will be asked about their food choice motives for the month before questionnaire completion.

Indices

Three scores will be calculated based on the FFQ at each time point:

- **Meat consumption.** Meat daily intake (in grams) will be calculated by summing daily intake for all the items of the FFQ that fall into the meat category.

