⁷ Chaltiel and others, 'Programme National Nutrition Santé - Guidelines Score 2 (Pnns-Gs2): Development and Validation of a Diet Quality Score Reflecting the 2017 French Dietary Guidelines', *British Journal of Nutrition*, 122.3 (2019), 331–42 <<https://doi.org/10.1017/S0007114519001181>>.

⁸ [name] and others, 'Food Choice Motives and the Nutritional Quality of Diet during the COVID-19 Lockdown in France', *Appetite*, 157.105005 (2021) <<https://doi.org/10.1016/j.appet.2020.105005>>.

(H4) and animal welfare motives (H4), as dependant variables, time (T0, T1 / T0, T2), group (intervention, control), time*group interaction as fixed effects and participant as random effect. These models will be adjusted for gender, age and BMI in order to control for potential confounding effects. We will report adjusted mean differences between T1 and T0, and between T2 and T0 for the intervention and the control group.

If we find a significant effect of the intervention on meat consumption, i.e., time*group interaction is significant in the models above, we will run two additional models on the intervention group only to investigate whether the level of the challenge (i.e., (i) no meat, (ii) meat 3 times a week, (iii) meat 6 times a week) differentially influence meat consumption reduction. The first linear mixed model will be run with meat consumption as dependant variable, time (T0, T1 / T0, T2), level (i, ii, iii), time*level interaction as fixed effects and participant as random effect. We will report adjusted mean differences between T1 and T0, and between T2 and T0 for each level. In the second linear mixed model, we will substitute the level of the challenge by the difference between baseline meat consumption frequency (in times per week) and the level of the challenge (continuous variable).

All statistical analyses will be performed using SAS version 9.4 (SAS Institute, Inc., 2012 SAS® 9.4. Cary, NC). The proc mixed will be used for mixed models. The level of significance will be set at $p < 0.05$ for all pre-registered analyses.

Data exclusion

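### The second challenge-level model, fitted in the intervention arm only, cannot show an effect of goal difficulty: its baseline-minus-goal predictor has no named source, is open to regression to the mean if that source is the T0 FFQ, and mixes baseline intake with goal

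*Combined protocol and SAP*

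**What the plan says.** If the time*group interaction for meat consumption is significant, Statistical models continues: "we will run two additional models on the intervention group only to investigate whether the level of the challenge" affects the reduction in meat consumption. The first of these models uses the three goals as categories. In the second, "we will substitute the level of the challenge by the difference between baseline meat consumption frequency (in times per week) and the level" chosen, as a continuous variable. The terms are time (T0 with T1, or T0 with T2), the gap and their interaction, with participant as random effect.

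The outcome comes from the FFQ. Under Measured variables, "daily intake will be calculated by multiplying the daily frequency by the estimated portion size". Under Indices, meat intake in grams is "calculated by summing daily intake for all the items of the FFQ that fall into the meat category".

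On goals, the description of the challenge states: "Eligible participants that will give their informed consent will be able to choose their goal for the challenge for one month". One of the options is "meat 6 times a week (which will need to be lower than current consumption". How current consumption is established is not described. The inclusion questionnaire list ends with "place of living, dieting status and type of diet" and contains no meat-frequency item. Under Randomization, "A 1:1 randomisation sequence will be generated before recruitment"; when allocation is disclosed is not stated.

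The 5% level applies to every pre-registered analysis, and Exploratory analysis reserves that label for analyses that are not pre-registered.

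**The concern.** T0 grams are T0 frequency times portion size. If the T0 FFQ also supplies the baseline frequency, the same T0 error and month-to-month fluctuation enter the gap with a plus sign and the change with a minus sign. A participant who over-reports, or eats unusually much meat, in the T0 month gets a larger gap and a larger apparent fall, even if the goal does nothing. With only one arm, nothing subtracts this.

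A second difficulty does not depend on the source. The gap is baseline minus goal, so heavier eaters have larger gaps. If everyone cut the same percentage regardless of goal, they would also show larger falls in grams, and the model would report a gap effect.

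At stake is one message: a significant slope would stand as a pre-registered finding that more demanding goals produce larger reductions. The model runs only when the trial has succeeded on meat consumption, which is when such a message is most likely to be used.

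**Working it through.** **Size of the arm.** The plan gives no figure for the gap model, so the sample size is the starting point. From Sample size rationale: f = 0.10, two groups, three measures, alpha 0.05, power 0.80, N = 164. Assuming a correlation of 0.5 between measures (not stated), noncentrality = f²·N·m/(1−ρ) = 0.01 × 164 × 3 / 0.5 = 9.84, with 2 and 324 degrees of freedom. Power is 0.805, so 164 is reproduced. Allocation at 1:1 gives 164/2 = 82 in the intervention arm. Recruiting 200 covers 18% attrition (164/0.82 = 200).

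**Reduction to a regression.** With two complete time points and a random intercept, the time*gap coefficient equals the ordinary least-squares slope of change on gap.

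**Assumptions, none in the documents.** Meat frequency mean 8, SD 4 per week; intake mean 120, SD 50 g/day; a uniform fall of 20 g/day unrelated to goal; goals random among 0, 3 and 6 below baseline frequency. ρ is the T0-T1 correlation and r the frequency-grams correlation.

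**Expected slope with the T0 FFQ as source.** Cov(change, T0 frequency) = ρ·r·SD_F·SD_Y − r·SD_F·SD_Y = −(1−ρ)·r·4·50. If goals were unrelated to frequency, Var(gap) = 4² + Var(goal) = 16 + (9+0+9)/3 = 22.
- ρ = 0.5, r = 0.8: −0.5 × 0.8 × 200/22 = −3.6 g/day per weekly occasion (simulated −4.2).
- ρ = 0.8, r = 0.5: −0.2 × 0.5 × 200/22 = −0.9 (simulated about −1.05).

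The simulated slopes are steeper because goals must lie below baseline, which narrows the spread of the gap.

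**False-positive rate at p<0.05, n = 82, T0 FFQ as source, no goal effect** (3,000 trials per cell):

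| r | ρ = 0.3 | 0.5 | 0.7 | 0.8 |
|---|---|---|---|---|
| 0.5 | 59% | 45% | 29% | 20% |
| 0.7 | 87% | 74% | 51% | 36% |
| 0.8 | 94% | 85% | 62% | 46% |
| 0.9 | 99% | 92% | 72% | 55% |

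Virtually all rejections point to larger gap, larger reduction. A different set of assumptions (mean 9, SD 3.5 per week, 120 g per occasion, FFQ reliability 0.9 down to 0.5) gives slopes of −1.3 to −6.2 and rates of 36-96%.

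**Dependence on the source.** If the source's deviation from usual intake correlates 0 / 0.25 / 0.5 with that of the T0 FFQ, the rates are about 5% / 6-16% / 8-50%.

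**If goals do act.** With the T0 FFQ as source, participants who truly move 0% / 25% / 50% of the way to their goal appear to move 16-58% / 38-69% / 59-80%. The bias fades near full compliance.

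**Baseline-goal mixing.** Let everyone cut 30% regardless of goal, with an independent-error source. The expected slope is about −0.3·ρ·r·200/22. At ρ = 0.3, r = 0.5 this is −9/22 = −0.41; at ρ = 0.8, r = 0.9 it is −43.2/22 = −1.96. Rejection is 6-75%, and 75-100% with the T0 FFQ as source. Unlike regression to the mean, this part grows as the T0-T1 correlation rises.

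**Check on alternatives.** A time*gap*group contrast in both arms brings the regression-to-the-mean false positives to 4-6%. It does not remove the mixing, because a percentage cut occurs only in the intervention arm and scales with baseline. A both-arm group*goal test adjusted for T0 intake and T0 frequency holds 4-6% in every pattern tried but one: a uniform 30% cut with goals tracking true usual intake (6-16%). The corresponding adjusted model in the intervention arm alone gives 26-97% when goals track usual intake.

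**The case against.** The strongest reply is that the documents do not establish the T0 FFQ as the source. The inclusion list is not exhaustive: BMI is an eligibility criterion and a covariate, yet is not listed. Goals are set in times per week against current consumption at enrolment, whereas the FFQ yields item-level daily frequencies and no weekly meat count is defined from it. An enrolment answer is therefore a natural reading, and with independent error it brings the false-positive rate to about 5%. This stands. A reader might infer that the planned analysis is certainly biased; the documents support only an unnamed source for which the one described instrument is vulnerable. An enrolment answer given close to T0 could also share some of its error.

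Second, the gap is openly defined as the reduction required, and under a uniform percentage cut people with larger gaps really do fall by more grams. That is a true association, and only a causal reading of it would be wrong. This also stands, but the stated purpose is to learn whether challenge level influences reduction, and this slope cannot answer that.

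Third, the model is conditional and additional, and being pre-registered does not make it confirmatory. This limits the severity but does not remove the point.

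**Conclusion.** The point holds as a minor-to-moderate secondary issue. The direction is secure if the T0 FFQ is the source: a spurious slope of larger gap, larger reduction. Its size is not secure. The range of about 20-99% rests on assumed means, SDs and correlations and does not predict this trial's error rate. With an independent-error source the artefact largely disappears, but the slope still cannot be read as an effect of challenge level.

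A reader might go further and doubt the main result. The documents do not support that: the model serves none of H1-H4, runs only after a significant time*group interaction, and touches neither the randomised comparison nor the sample size.

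**What to change.** - State which instrument and item supply baseline meat frequency, and how it is converted to times per week.
- Replace the arm-only gap test by a model in both arms: T1 meat intake (and separately T2) on group, goal, T0 intake, T0 frequency, and the interaction of each of the last three with group. Test group*goal. This requires control-arm goals recorded before or blind to allocation. The plan describes goal choice for all eligible consenting participants but not its timing relative to disclosure, so that should be stated too.
- A time*gap*group contrast is simpler, but is adequate only against regression to the mean.
- If control-arm goals are not usable, keep the intervention-arm slope as descriptive, with no p-value claim about goal difficulty. Adjusting for T0 intake and T0 frequency within that arm is not a reliable substitute.
- Report the result as a non-randomised secondary association.

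The cost is SAP wording, with no new measurement if goals are recorded at enrolment. The drawback is low power. If each weekly occasion of lower goal truly cuts 4 g/day more (6 × 4 = 24 g/day between no meat and six times), group*goal has 20-48% power with goals random below baseline and 10-22% with goals tied to it. At 2 g/day power is 5-16%, and at 8 g/day 24-96%. A non-significant result should not be read as no effect of goal.

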available data points only. Sensitivity analyses will be conducted using multiple imputation, first on missing values only and then on missing and implausible values¹².

Exploratory analysis

Any supplementary analysis that is not pre-registered here will be described as an exploratory analysis.

¹² Peng Li and Elizabeth A Stuart, 'Best (but Oft-Forgotten) Practices : Missing Data Methods in Randomized Controlled Nutrition Trials', *American Journal of Clinical Nutrition*, 109 (2019), 504–8.

Appendix 1. Study design
